6.8 Physical Exam

The investigator (or designee) will perform a physical exam at Baseline and Follow-up to assess stage of lipedema and lymphedema, presence of edema at Sites 1-6 (where circumferential measurements were taken), and presence/absence of clinical symptoms. It is important to note that progression to lipo-lymphedema (lipedema with swelling), a requirement of this study, typically develops during Stage 2/3 of lipedema.

- Lipedema Stage:
 - Stage 1 = Smooth/normal skin surface with enlarged hypodermis/homogenous thickening of the subcutis.
 - Stage 2 = Bumpy, wave-like skin surface with indentations/nodular structures (masses, lipomas, angiolipomas) in the thickened subcutis.
 - Stage 3 = An increase in nodular changes/deformations and overhanging masses of tissue (especially on the thighs and around the knees).
- Lymphedema Stage:
 - Stage 0 = Latent or subclinical condition where swelling is not yet evident despite impaired lymph transport, subtle alterations in tissue fluid/composition, and changes in subjective symptoms.
 - Stage 1 = Early accumulation of fluid relatively high in protein content which subsides with limb elevation. Pitting may occur.
 - Stage 2 = Limb elevation alone rarely reduces the tissue swelling and pitting is manifest. Later in state 2, the limb may not pit as excess subcutaneous fat and fibrosis develop.

- Stage 3 = Symptoms of lymphostatic elephantiasis where pitting can be absent and trophic skin changes such as acanthosis, alterations in skin character and thickness, further deposition of fat and fibrosis, and warty overgrowths have developed.
- Edema at Sites 1-6:
 - None = No pitting
 - 1+ = Trace: Tissue returns to normal almost immediately
 - 2+ = Mild: Tissue returns after 15-59 seconds
 - 3+ = Moderate: Tissue returns after 1-2 minutes
 - 4+ = Severe: Tissue returns after > 2 minutes
 - NA = Tissue no longer pits due to induration

6.9 QOL, Symptoms, Mobility & Pain Assessments

The following assessments will be completed by the subject at the Baseline and Follow-up visits. Subjects will be instructed to answer all of the items (i.e., questions or statements) presented. Prior to departure, study personnel will review each assessment for missing data to ensure the subject addressed each item.

6.9.1 QOL

The RAND 36-Item Health Survey (Version 1.0) taps eight health concepts: physical functioning, bodily pain, role limitations due to physical health problems, role limitations due to personal or emotional problems, emotional well-being, social functioning, energy/fatigue, and general health perceptions. It also includes a single item that provides an indication of perceived change in health. (*Appendix A*)

6.9.2 Mobility

The PROMIS Mobility v2.0 (29 November 2016) is a 15-item questionnaire completed by subjects that focuses on activities of physical mobility such as getting out of bed/chairs to activities such as running. The adult Mobility measures include selected items from the full Physical Function item bank. (*Appendix B*)

6.9.3 Pain Interference & Symptoms

To assess pain and symptoms related to lipo-lymphedema (lipedema with swelling), subjects will complete:

- The PROMIS Pain Interference - Short Form 6b v1.0 (2 May 2016) measures self-reported consequences of pain on relevant aspects of a person's life and may include the extent to which pain hinders engagement with social, cognitive, emotional, physical, and recreational activities. (*Appendix C*)
- The Wong-Baker Faces Pain Rating Scale is a pain scale that shows a series of faces ranging from a happy face at 0, or "no hurt," to a crying face at 10, which represents "hurts like the worst pain imaginable." Based on the faces and written descriptions, the patient chooses the face that best describes

their level of pain associated with lipo-lymphedema (lipedema with swelling). (*Appendix D*)

- Subjects will be asked to rate their perceptions of swelling, heaviness, pain, fatigue, tenderness, and tightness independently for each leg using a 10-point numerical rating scale where 0 represents none/not present and 10 is worst imaginable.³ (*Appendix E*)

6.10 Treatment

Following randomization, collection of measurements, and the completion of questionnaires, patients will be trained on the conservative care prescribed by the investigator (or designee).

Patients randomized to the Flexitouch Plus will obtain a device through standard commercial means (via self-pay, patient assistance, or insurance programs). The standard prescription of ‘Full Leg and Core (L1)’ with daily simultaneous bilateral lower extremity treatment (~60 minutes) at normal pressure levels will be used unless alternate programming is selected by the investigator. Alternate programming (e.g., twice daily, high pressure, additional supplemental lower leg program, etc.) may be used at the investigators discretion if a subject reports inadequate control of lymphedema symptoms prior to the next study visit. While alternate programming is not expected to be necessary, it is important subjects have access to the best care possible at all times in a “real world” study.

Once the prescription is submitted/processed at the Baseline visit, device shipment and training on device use must take place within 60 days or the subject will not be enrolled in the study.

At the Follow-up visit, some or all subjects may receive an in-clinic treatment with Flexitouch Plus after the Follow-up data collection is complete. Additional circumferential (including 4 sites on each leg, 1 site at the hips, and 1 site at the waist using a Gulick II tape measure) and bioimpedance (including whole body ECW/TBW ratio, as well as segmental ratios for the Right/Left Arm, Right/Left Leg, and Trunk) measurements may be collected and recorded immediately after completion of the in-clinic Flexitouch Plus treatment.

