4.4 Treatment Assignment and Duration

Eligible patients will be randomized (1:1) using sealed envelopes to one of the following treatment cohorts:

- Conservative care alone (may include 30-40 mmHg graduated compression up to waist, dietary counseling, exercise, and/or referral for CDT); or
- Flexitouch Plus with conservative care.

Following randomization, a product demo may take place to confirm the subject is able to tolerate prescribed care.

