6.5 Randomization

If the subject meets all of the inclusion criteria and none of the exclusion criteria, they will be randomly assigned to Flexitouch Plus with conservative care or conservative care alone. Randomization codes will be generated in a permuted block design. The block size will be balanced within each block, and will maintain a 1:1 ratio between the treatment groups.

The randomization code will be distributed by sealed envelope and assigned sequentially as soon as an eligible subject completes the Baseline measurements. The appropriate staff member will obtain the next sequentially sealed randomization envelope and open it while the subject is present.

The randomization assignment cannot be changed or chosen by the subject or the investigator. The randomization envelope, as well as evidence of treatment group assignment, should be placed in the subject's binder.

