Appendix E. NRS Symptom & Pain Scale

VISUAL ANALOG SCALE TO EVALUATE SYMPTOM SEVERITY

ID: _____ **DATE:** _____

We are trying to find out about your lipo-lipedema symptoms. There are 12 items we would like you to respond to. This should take less than 1 minute of your time.

DIRECTIONS: You are asked to circle a number on each of the following lines to indicate how you are feeling RIGHT NOW about symptoms in your left and right leg (these questions are not asking about other parts of your body).

PLEASE COMPLETE THE FOLLOWING ITEMS WHILE THINKING ABOUT WHILE YOUR LEFT LEG:

- | | | | | | | | | | | | | |
|------------------|---|---|---|---|---|---|---|---|---|---|----|-----------------------------|
| 1. No swelling | 0 | 1 | 2 | 3 | 4 | 5 | 6 | 7 | 8 | 9 | 10 | Worst imaginable swelling |
| 2. No heaviness | 0 | 1 | 2 | 3 | 4 | 5 | 6 | 7 | 8 | 9 | 10 | Worst imaginable heaviness |
| 3. No pain | 0 | 1 | 2 | 3 | 4 | 5 | 6 | 7 | 8 | 9 | 10 | Worst imaginable pain |
| 4. No fatigue | 0 | 1 | 2 | 3 | 4 | 5 | 6 | 7 | 8 | 9 | 10 | Worst imaginable fatigue |
| 5. No tenderness | 0 | 1 | 2 | 3 | 4 | 5 | 6 | 7 | 8 | 9 | 10 | Worst imaginable tenderness |
| 6. No tightness | 0 | 1 | 2 | 3 | 4 | 5 | 6 | 7 | 8 | 9 | 10 | Worst imaginable tightness |

PLEASE COMPLETE THE FOLLOWING ITEMS WHILE THINKING ABOUT YOUR RIGHT LEG:

- | | | | | | | | | | | | | |
|----------------|---|---|---|---|---|---|---|---|---|---|----|---------------------------|
| 1. No swelling | 0 | 1 | 2 | 3 | 4 | 5 | 6 | 7 | 8 | 9 | 10 | Worst imaginable swelling |
|----------------|---|---|---|---|---|---|---|---|---|---|----|---------------------------|

VISUAL ANALOG SCALE TO EVALUATE SYMPTOM SEVERITY

ID: _____ **DATE:** _____

2. No heaviness	0	1	2	3	4	5	6	7	8	9	10	Worst imaginable heaviness
3. No pain	0	1	2	3	4	5	6	7	8	9	10	Worst imaginable pain
4. No fatigue	0	1	2	3	4	5	6	7	8	9	10	Worst imaginable fatigue
5. No tenderness	0	1	2	3	4	5	6	7	8	9	10	Worst imaginable tenderness
6. No tightness	0	1	2	3	4	5	6	7	8	9	10	Worst imaginable tightness

THANK YOU!

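### Sections 6.5 and 6.10 do not clearly require the Baseline questionnaires to be finished before the envelope is opened in front of the subject

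*Combined protocol and SAP*

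**What the plan says.** Five places in the combined protocol and SAP bear on the order of events at the Baseline visit.

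- **6.5 Randomization.** The code is "assigned sequentially as soon as an eligible subject completes the Baseline measurements". Staff then "obtain the next sequentially sealed randomization envelope and open it while the subject is present", so the subject learns her arm at that moment.
- **6.10 Treatment.** "Following randomization, collection of measurements, and the completion of questionnaires, patients will be trained on the conservative care". Three things come before training, and randomization is the first one named.
- **6.9 QOL, Symptoms, Mobility & Pain Assessments.** The questionnaires are tied to the visit only: "The following assessments will be completed by the subject at the Baseline and Follow-up visits". The one time limit within the visit is on checking: "Prior to departure, study personnel will review each assessment for missing data".
- **4.4 Treatment Assignment and Duration.** "Following randomization, a product demo may take place to confirm the subject is able to tolerate prescribed care". Nothing says where this falls relative to the questionnaires.
- **Table 1 (section 5.0).** The questionnaire rows stand above the Randomization row, and Training stands below it.

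Sections 4.1 and 13.2 show what depends on these answers. Two of the three primary endpoint groups, quality of life and symptoms/pain, are patient-reported. The primary analysis is the paired change from baseline within each arm. The between-arm ANCOVA uses the same baseline as a covariate.

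**The concern.** The trial is open to the subject. If she fills in the RAND-36, PROMIS Pain Interference, Wong-Baker and numerical rating forms after seeing her assignment, her Baseline is no longer a pre-allocation measurement. News of getting, or not getting, the device could colour her answers. The analyses in 13.2 cannot separate such a shift from a change over the treatment period.

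The instruments are not equally exposed. The 12 leg-symptom items ask the subject "to indicate how you are feeling RIGHT NOW about symptoms", so a momentary reaction can enter directly. The Wong-Baker form is also worded in the present tense. PROMIS Pain Interference looks back 7 days and many RAND-36 items look back 4 weeks, so they should be less sensitive. The same gap in ordering applies to the exploratory PROMIS Mobility form.

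**Working it through.** **Step 1: does *measurements* in 6.5 include the questionnaires?**

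| Place | Usage | Points to |
|---|---|---|
| 6.6 and 6.7 headings, Table 1 rows | *Measurements* means bioimpedance and circumference | Questionnaires not covered |
| 6.9 heading, Table 1 rows | The patient-reported instruments are *assessments* | Questionnaires not covered |
| 6.10 | Measurements and questionnaires are separate items | Questionnaires not covered |
| 13.2 | *Baseline measurement* stands for any outcome analysed | Questionnaires covered |

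The procedural sections lean one way and the statistical section the other. The text does not settle it.

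**Step 2: does another passage fix the order?** Sections 6.6 and 6.7 put bioimpedance and girth at the beginning of the visit, so those are safely ahead of the envelope. Section 6.10 gives no order among its three items. Table 1 lists the questionnaires above Randomization, but its rows are not a dependable time order: it lists circumference before bioimpedance, and 6.7 has the reverse. Section 6.9 fixes only the visit. A coordinator who takes girth and bioimpedance, opens the envelope, and then hands over the forms breaks no sentence of the protocol.

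**Step 3: how a shift would carry through.** Suppose knowledge of the arm moves the reported Baseline in one arm by d, measured in SDs of a single score, and that this movement is absent at Follow-up. If it persisted, part of it would cancel in the paired change. With baseline-to-follow-up correlation ρ and equal SDs:

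- size of bias in the paired change = d
- size of bias in the ANCOVA contrast = slope × d = ρ × d
- paired-test noncentrality = d√n / √(2(1−ρ)), with n − 1 degrees of freedom
- ANCOVA noncentrality = ρd / [√(1−ρ²) × √(2/n)], with 2n − 3 degrees of freedom

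Inputs from the plan are n = 15 per group (13.1) and two-sided α = 0.05 (13.2). The values of d and ρ are assumptions; the documents give neither. Example with d = 0.2 and ρ = 0.5: the paired noncentrality is 0.2 × √15 / 1 = 0.77, which gives 11.2%. The ANCOVA noncentrality is 0.10 / (0.866 × 0.365) = 0.32, which gives 6.1%. With no true effect and ρ from 0.5 to 0.8:

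| d (SD) | Paired bias (SD) | Paired false-positive rate | ANCOVA bias (SD) | ANCOVA false-positive rate |
|---|---|---|---|---|
| 0 | 0 | 5% | 0 | 5% |
| 0.1 | 0.1 | 6.5–8.8% | 0.05–0.08 | 5.3–6.4% |
| 0.2 | 0.2 | 11.2–20.8% | 0.10–0.16 | 6.1–10.9% |
| 0.5 | 0.5 | 43.8–81.2% | 0.25–0.40 | 11.9–42.1% |

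On a 0–10 item, an assumed shift of 0 to 1.0 point with a slope of 0.5 to 0.7 gives a bias of 0 to 1.0 point within the arm and 0 to 0.7 × 1.0 = 0.7 point between arms.

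**Step 4: a yardstick from the plan.** Section 13.1 aims for a half-width of about 0.40 SD with 15 subjects (30 legs) per group. This reproduces approximately if legs count as independent: (1.96/0.40)² = 24.01, so 25 legs, or 27 legs with the t distribution; 30 legs give 0.373 SD. A questionnaire scored once per subject has n = 15 and a half-width of 2.145/√15 = 0.554 SD. At ρ = 0.5 the SD of the change equals the SD of a single score, so a 0.2 SD shift is half of the 0.40 target and about 36% of 0.554.

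**The case against.** The strongest reply is that 6.5, the section that governs randomization, already places it after Baseline. Section 13.2 uses *baseline measurement* for every outcome, and Table 1 agrees with that order. On this reading the questionnaires come first and there is no problem. That reading is available and may be what was intended. What remains is that the procedural sections, which staff work from, use the word more narrowly.

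Several stronger readings are tempting, and the documents do not support them.

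- A reader might infer from 6.10 that the plan schedules the questionnaires after randomization. It does not: the sentence lists three things that precede training. Taken as a strict sequence, it would also put girth and bioimpedance after randomization, against 6.5, 6.6 and 6.7.
- A reader might infer that the forms are completed after a device demo. Section 4.4 makes the demo optional and no passage places it before the forms; the inference rests on silence.
- A reader might infer that the arms would be pushed in opposite directions. Nothing in the documents gives a direction or a size, and zero is possible.
- A reader might take the check before departure in 6.9 as leave to complete forms late. It sets the time of a missing-data review and nothing more.

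It is also fair to say that Follow-up answers come from women who know their arm whatever the Baseline order, and that 13.2 describes an exploratory study focused on estimation. Both stand. Neither is a reason to leave the Baseline open to the same influence when protecting it costs nothing.

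**Conclusion.** The finding is an ambiguity between 6.5 and 6.10, not a demonstrated bias. The plan does not clearly require Baseline patient-reported outcomes before the arm is known, and a site could comply with the text while collecting them afterwards. If that happened, a shift confined to Baseline would pass in full into the primary paired change and, multiplied by the baseline slope, into the ANCOVA. Both the size and the direction of any shift are unknown.

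The figures above rest on an assumed shift that includes zero, an assumed correlation of 0.5 to 0.8, no true effect, a shift in one arm only, and no carry-over of the shift to Follow-up. They show that even a modest shift would matter at 15 subjects per arm; they do not predict that one occurs. The numerical rating items are likely the most exposed and the 7-day and 4-week recall forms less so. Circumference and bioimpedance are not affected. The point deserves action because it concerns the baseline of primary endpoints and is almost free to close.

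**What to change.** In 6.5, state the order outright, for example: *The envelope is opened only after all Baseline measurements and all Baseline questionnaires have been completed and checked for missing items; any product demo takes place afterwards.* Reword 6.10 to the same order, with measurements and questionnaires first, then randomization, then training.

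The cost is one sentence in each of two sections, with the missing-item check done before the envelope is opened and not merely before departure. The visit, staff and forms stay the same. If sites already work this way, the sentence makes the practice verifiable.

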4.2 Subject Selection

The target population includes patients who have bilateral lipedema, meet the criteria listed below, and have provided informed consent.

4.2.1 Inclusion Criteria:

1. Female age 18-70 years.
2. Stage 2-3 (Schmeller Type 2-3) lipedema with secondary lymphedema.
3. Willing and able to follow prescribed care for study period.
4. Able to access (via self-pay, patient assistance, or insurance programs) prescribed care within 60 days of Baseline visit.

4.2.2 Exclusion Criteria:

1. BMI > 50.
2. Heart failure (acute pulmonary edema, decompensated acute heart failure).
3. Pacemaker or implantable cardioverter defibrillator (ICD).
4. Acute venous disease (acute thrombophlebitis, acute deep venous thrombosis, acute pulmonary embolism).
5. Severe peripheral artery disease (critical limb ischemia including ischemic rest pain, arterial wounds, or gangrene).
6. Active skin or limb infection/inflammatory disease (acute cellulitis, other uncontrolled skin or untreated inflammatory skin disease) on the arms or trunk.
7. Active cancer (cancer that is currently under treatment, but not yet in remission).
8. Poorly controlled kidney disease (glomerular filtration rate < 30 mls per minute), hypoproteinemia, pulmonary hypertension, hypothyroidism, cyclic edema, or Munchausen Syndrome.
9. Any circumstance where increased lymphatic or venous return is undesirable.

10. Currently pregnant or trying to become pregnant.

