5.0 Study Assessment

Case Report Forms (CRFs) and Data Clarification Forms (DCFs) will be used for data collection and query handling. The Investigator will ensure the accuracy, completeness, and timeliness of the data recorded.

All data will be entered into an Excel spreadsheet and validated to confirm integrity of data entry. Data may be transferred to an electronic data capture system at some point. When all data have been coded, validated, and signed, the database will be locked (password protected with copy saved as PDF), and available for analysis.

The study schedule of activities is shown in Table 1.

Table 1. Schedule of Activities

Procedures	Baseline (Day 0)	Follow-up (4-12 weeks)
Informed Consent	X	
Demographics & Medical History	X	
Inclusion/Exclusion Assessment	X	
Pregnancy Test (if applicable)	X	
Vitals	X	X
Physical Exam	X	X
Circumferential Measurements	X	X [^]
Bioimpedance Measurements	X	X [^]
QOL Assessment (RAND SF-36)	X	X
Mobility Assessment (PROMIS Mobility)	X	X
Symptom & Pain Intensity Assessment (PROMIS Pain Intensity, NRS Pain & Symptom Scale, Wong-Baker Faces Scale)	X	X
Randomization	X	
Training on Flexitouch Plus and/or Conservative Care*	X	
Adverse Event, Complication, & Device Observation Assessment	X	X

* If subject is unable to obtain prescribed care and complete training on use within 60 days of the Baseline visit (e.g., due to insurance coverage/scheduling delays, etc.), the subject will be considered a screen failure.
 
[^] Optional: Circumferential and bioimpedance measurements may be taken again after an in-clinic treatment with Flexitouch Plus.
		

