6.3 Laboratory Testing

Any women who are not surgically sterile or ≥ 1 year post-menopause will be tested for pregnancy according to the site specific procedures at the Baseline visit. If the pregnancy test is positive, the subject will not be enrolled in the study.

Subjects must agree to use one of the following forms of birth control prior to starting and during treatment with the Flexitouch:

- Abstinence (not having sexual relations with a person of the opposite sex)
- Implantable hormone (e.g. Norplant)
- Intrauterine Device
- Male partner must have a vasectomy
- Female sterilization
- Hormonal injection
- Oral contraceptives

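### Exclusion 6 does not name the legs although the device treats the legs; secondarily, no health check is required before first home use, up to 60 days after Baseline

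*Combined protocol and SAP*

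**What the plan says.** Exclusion 6 in section 4.2.2 reads: "Active skin or limb infection/inflammatory disease (acute cellulitis, other uncontrolled skin or untreated inflammatory skin disease) on the arms or trunk". It is the only exclusion that names infection. Exclusion 9 is a general clause: "Any circumstance where increased lymphatic or venous return is undesirable".

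Section 6.10 prescribes a full-leg-and-core programme "with daily simultaneous bilateral lower extremity treatment (~60 minutes) at normal pressure levels", unless the investigator selects other settings.

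On timing, the Table 1 row "Inclusion/Exclusion Assessment" is marked under Baseline only, and the one other scheduled visit is Follow-up. Randomisation takes place at Baseline, once the measurements are complete (6.5). The device is then obtained commercially, and under 6.10 "device shipment and training on device use must take place within 60 days or the subject will not be enrolled in the study". The Table 1 footnote sets the same limit: "If subject is unable to obtain prescribed care and complete training on use within 60 days of the Baseline visit", she is counted as a screen failure. Both rules concern access and training. Neither concerns health on the day that treatment starts.

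**The concern.** An exclusion list for a compression device should clearly bar active infection where the device is applied. Here the site qualifier covers the trunk, which the programme does treat, and the arms, but not the legs. A coordinator who applies the list item by item could pass a woman with active cellulitis of one leg. This can happen at Baseline and does not depend on any delay.

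The delay adds a second, smaller gap. Acute venous thrombosis, decompensated heart failure and active infection are states that can begin after Day 0. The plan treats them as reasons not to enrol, yet does not require anyone to ask about them again before daily leg compression begins at home. What is at stake is the safety of a few women, not the validity of an estimate.

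**Working it through.** The plan states no figure to reproduce. The first part is a reading of the text; the second needs only simple arithmetic.

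**Exclusion 6 against the treated area**

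1. Treated area: both legs and the core (6.10).
2. Sites named at the end of exclusion 6: arms and trunk. The overlap with the treated area is the trunk.
3. The word *limb* early in the criterion could be taken to include the legs. However, acute cellulitis is given as an example directly before the site qualifier, and the natural reading applies the qualifier to it. At best the criterion is ambiguous about leg cellulitis.
4. Exclusion 9 could catch leg cellulitis, but it names no condition and so depends on judgment.
5. The plan regards infection as relevant in this population. Section 2.1 says that the swelling may lead to infection, 6.11.4 logs cellulitis as a complication, and 8.1 lists cellulitis as a less likely treatment risk.

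**Interval from eligibility check to first home use**

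Inputs: a 60-day limit (6.10, the Table 1 footnote and inclusion 4); 15 analysable subjects per arm plus 3 replacements (13.1).

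- Longest interval: 60 / 7 = 8.6 weeks. The typical interval is not stated.
- Women in the device arm: 15 + 3 = 18.
- Ceiling on time between check and start: 18 × 60 = 1,080 woman-days; 1,080 / 365.25 = 2.96 woman-years. This requires every woman to start on day 60.
- Assumed mean interval of 14 days: 18 × 14 = 252 woman-days; 252 / 365.25 = 0.69 woman-years.
- Assumed mean interval of 30 days: 18 × 30 = 540 woman-days; 540 / 365.25 = 1.48 woman-years.

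The 14- and 30-day values are assumptions. All these totals measure elapsed time, not harm. Without an event rate they cannot be turned into a number of women affected.

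**What the plan provides in the interval**

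- The product demo (4.4) is optional and tests tolerance.
- Close monitoring (8.3), individual case review by the investigator (11.1) and withdrawal for a change in health (7.1) are general oversight. None is tied to the start of device use.
- The pregnancy test has the same timing, since women who need one "will be tested for pregnancy according to the site specific procedures at the Baseline visit". The contraception agreement in 6.3 spans the interval, so pregnancy is not part of this point.

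**The case against.** The strongest reply is that this is on-label, post-market use of a cleared device that is prescribed and supplied commercially with training. Section 6.11.5 refers to instructions for use that are not among the documents, and screening for contraindications may well sit there or in the supplier's training. That stands as a limit: what is shown is that the protocol is silent, not that nobody asks.

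Section 8.1 adds that device pressures do not exceed those of compression garments, and conservative care continues without a re-check too. This bears on the size of the risk, but the plan still chose to exclude these conditions.

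The legs may also have been left out on purpose, because section 2.3.1 lists stasis dermatitis and leg ulcers among the device's indications. That could explain not barring chronic leg skin disease. It does not explain leaving acute leg cellulitis unclear.

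A single check before first use would not catch an event that arises later, during weeks of home treatment. That is true, and it is one reason to treat the timing point as minor. At Baseline, the physical exam (6.8) includes the leg sites, so an attentive investigator would probably notice cellulitis and apply exclusion 9.

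A reader might infer that women go through an unmonitored interval, that some will be harmed, or that the results will be biased. The documents support none of these: there is general oversight, no event rate is given, and no effect on an endpoint is shown. Nor do they support a separate checklist before the optional in-clinic session at Follow-up, because Table 1 already has a physical exam and an adverse event assessment at that visit.

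**Conclusion.** The main point holds on the text. Exclusion 6 does not clearly bar active infection of the limbs that the device treats, and exclusion 9 fills the gap only by judgment. The timing point also holds but is minor: up to 60 days may pass between the only eligibility assessment and first home use, for about 18 women at most, with no required question about new acute illness.

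This rests on two conditions: that the site qualifier in exclusion 6 applies to cellulitis, and that no screening outside the documents already closes the gap. Few women would be expected to be affected, though the documents do not allow a number. Sample size and analysis are untouched.

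**What to change.** 1. **Exclusion 6.** Add the legs to the sites named at the end of the criterion. If the sponsor wishes to keep women with stasis dermatitis, which is a listed indication, say so in the same line. The cost is a few words in an amendment.
2. **Section 6.10.** Before first home use, site staff ask and document a short status question covering acute venous disease, decompensated heart failure and active infection, including of the legs. If a commercial trainer delivers the training, the question can be put by phone; the documents do not say who trains. If the answer is positive, withhold the device until the investigator clears it, and keep following the woman in her randomised arm. State that a medical hold is not a failure of access under the Table 1 footnote, so that she is not reclassified as a screen failure.

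The cost of the second change is a few minutes of site time per woman. At an assumed 5 minutes, 18 × 5 = 90 minutes, or 1.5 hours over the whole trial. It needs no extra visit and no routine test.
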